- If an AE develops during infusion, the infusion may be slowed or stopped as per investigator's decision.
 - Most reactions to plasma are relatively minor and the infusion can generally be continued. Infusion site burning and non-allergic systemic effects can generally be managed with slowing of the infusion. Infusion can generally be continued in cases of itching or hives after pausing the transfusion, administering antihistamines, and observing the patient for worsening.
 - Severe allergic reactions such as, bronchospasm and hypotension, and may require discontinuation of the infusion.

Concomitant medications will be documented on the CRF

- Prescription medications
- Over the counter medications

- Herbal treatments/nutritional supplements
- Blood products

Statistical considerations

Statistical Analysis

This is a pilot study focused on determining the protocol feasibility with limited subject enrollment. Therefore, statistical analysis will include descriptive summaries of both the primary and secondary outcomes of interest. For continuous variables we will determine: median, minimum and maximum values. Categorical variables will be summarized by the frequency. Unless otherwise indicated, percentages in tables will be column percentages, using the total number of observations in the population ($n=10$), as the denominator. Percentages will be rounded to one decimal place, and thus may not always add up to exactly 100%. Clinical laboratory values will be first reported in using International System of Units (SI).

Analysis of AE data

Analysis of AE data will primarily be descriptive based on MedDRA coding of events. The proportion of subjects experiencing an SAE and the proportion experiencing a Grade 3 or higher AE will be measured.

Analysis of SARS-CoV-2 viremia

Analysis of SARS-CoV-2 viremia will primarily be descriptive, comparing the viremia levels at days 0,1,3,7 and 14 between the subject recipients.

Analysis of research biomarkers

Analysis of biomarker tests performed in the research lab such as antibody titers, cytokine levels will primarily be descriptive, comparing the titers at days 0,1,3,7 and 14 between subject recipients.

Endpoints

Primary Endpoint:

1. Feasibility of performing study pathway consisting of consenting convalescent donors, harvesting convalescent plasma, application for FDA eIND and administering convalescent plasma to the patients

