The study enrollment and dosing will be stopped and an ad hoc review will be performed if any of the specific following events occur or, if in the judgment of the study physician, subject safety is at risk of being compromised:

1. Death within one hour of plasma infusion
2. Occurrence of a life-threatening allergic/hypersensitivity reaction (anaphylaxis), manifested by bronchospasm with or without urticaria or angioedema requiring hemodynamic support with pressor medications or mechanical ventilation. , TRALI, TACO
3. One subject with an SAE associated with study product.
4. Two subjects with a Grade 3 or higher lab toxicity for the same parameter associated with study product.
5. An overall pattern of symptomatic, clinical, or laboratory events that the medical monitor, ISM, or SMC consider associated with study product and that may appear minor in terms of individual events but that collectively may represent a serious potential concern for safety.
6. Any other event(s) which is considered to be a serious adverse event in the good clinical judgment of the responsible physician. This will be appropriately documented.

Upon completion of this review and receipt of the advice of the ISM, the IRB will determine if study entry or study dosing should be interrupted or if study entry and study dosing may continue according to the protocol.

Halting Criteria/Rules for Subject Infusion

Infusion of study drug will be halted if any of the following manifestations of anaphylaxis develop and will not be restarted:

- Skin or mucous membrane manifestations: hives, pruritus, flushing, swollen lips, tongue or uvula
- Respiratory compromise: dyspnea, wheezing, stridor, hypoxemia
- A decrease in systolic blood pressure to < 90 mmHg or >30% decrease from baseline or a diastolic drop of >30% from baseline.

- Tachycardia with an increase in resting heart rate to > 130bpm; or bradycardia <40 that is associated with dizziness, nausea or feeling faint.
- Any other symptom or sign which in the good clinical judgment of the study clinician or supervising physician warrants halting the infusion. For example, the rapid onset of gastrointestinal symptoms, such as nausea, vomiting, diarrhea, and cramps, for instance, may be manifestations of anaphylaxis and may warrant an immediate halt prior to meeting full SAE criteria

Ethics/Protection of human subjects

Ethical Standard

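### The treatment section lets the infusion continue after itching or hives; the infusion halting rule lists the same two signs and bars a restart

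*Combined protocol and SAP*

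**What the plan says.** The Combined protocol and SAP deals with reactions during the infusion in two places.

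**Investigational treatment-plasma administration.** If an adverse event develops, "the infusion may be slowed or stopped as per" the investigator decides. The sub-items then grade the response:
- In general: "Most reactions to plasma are relatively minor and the infusion can generally be continued".
- For the skin signs: "Infusion can generally be continued in cases of itching or hives after pausing the transfusion, administering antihistamines, and observing the patient for worsening".
- For the other end of the scale: "Severe allergic reactions such as, bronchospasm and hypotension, and may require discontinuation of the infusion".

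**Safety Oversight, Halting Criteria/Rules for Subject Infusion.** The lead-in is mandatory: "Infusion of study drug will be halted if any of the following manifestations of anaphylaxis develop and will not be restarted". The first item on its list reads "Skin or mucous membrane manifestations: hives, pruritus, flushing, swollen lips, tongue or uvula". Later items cover respiratory signs, blood pressure (including "A decrease in systolic blood pressure to < 90 mmHg or >30% decrease from baseline"), heart rate, and any other sign that the clinician judges to warrant a halt.

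The word anaphylaxis also appears in Halting Criteria for the Study, item 2, as a "life-threatening allergic/hypersensitivity reaction (anaphylaxis), manifested by bronchospasm with or without urticaria".

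**The concern.** Pruritus is itching, so both places address the same two signs. One allows the infusion to go on after a pause; the other ends it for good.

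This is a patient-safety rule, and bedside staff have to apply it at once. As it stands, two recipients with the same reaction could be handled differently, each with protocol text in support.

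Oversight is affected too. Under Study monitoring, monitors verify that investigators comply with the protocol, and a departure from approved procedures is defined as a protocol deviation. With two rules in force, a monitor cannot tell whether a restart after hives is one.

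The reaction is foreseeable from the document itself: rash is named among the risks of plasma and under transfusion reactions in the safety endpoints, and the treatment section addresses hives directly.

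**Working it through.** The protocol states no figure on this point, so there is none to reproduce. The main check is a comparison of the two texts.

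| | Plasma administration section | Infusion halting rule |
|---|---|---|
| Trigger | Itching or hives | Any one listed manifestation; hives and pruritus are listed |
| Action | May generally continue after a pause, antihistamines and observation | Halt, no restart |
| Force | Permissive | Mandatory |
| Severity condition | Set among minor reactions, apart from severe ones | No diagnosis, grade or second sign; lead-in mentions anaphylaxis |
| Cross-reference or precedence | None | None |

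1. **Overlap.** The skin and mucosal item names six signs: hives, pruritus, and flushing, then swelling of the lips, tongue or uvula. Two of the six (hives and pruritus) carry both instructions.
2. **Can both rules be met?** Yes, but only by never using the permission. Staff who halt and do not restart breach neither section. Staff who pause, treat, observe and resume follow the first section and breach the second as written.
3. **Does the word anaphylaxis settle it?** Clinical judgment is attached only to the last item on the halting list. No such condition is written for hives or pruritus. Item 2 of the study-level criteria describes a life-threatening event with bronchospasm, in which urticaria is optional. That is a trigger for stopping the study, where a higher bar may be intended, and it does not define the term for the infusion rule.
4. **Lesser tension.** The first section leaves stopping to the investigator and says that hypotension may require it. The halting rule makes a halt mandatory at its stated blood pressure falls. Smaller falls stay discretionary.

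**How often the situation could arise.** The planned number of recipients is 10 (Protocol Summary). No reaction rate is given, so r, the share who develop itching or hives, is assumed. The chance of at least one case is 1 − (1 − r)^10:

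| r (assumed) | 1 − (1 − r)^10 |
|---|---|
| 1% | 1 − 0.99^10 = 9.6% |
| 3% | 1 − 0.97^10 = 26.3% |
| 5% | 1 − 0.95^10 = 40.1% |
| 10% | 1 − 0.90^10 = 65.1% |
| 20% | 1 − 0.80^10 = 89.3% |

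**Illustration for the feasibility count.** Primary Objective item 1a counts recipients who complete the infusion and are evaluable, with 6-7 of 10 as the mark. Suppose a share b = 0.90 would otherwise complete, a share h is halted for good under one rule but continued under the other, and every halted infusion is a non-completion. Then the count is Binomial(10, p) with p = b(1 − h):

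| h (assumed) | p | P(at least 6) | P(at least 7) |
|---|---|---|---|
| 0 | 0.900 | 0.998 | 0.987 |
| 5% | 0.855 | 0.991 | 0.955 |
| 10% | 0.810 | 0.973 | 0.896 |
| 20% | 0.720 | 0.882 | 0.702 |

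Both b and h are assumptions. At b = 0.90 the effect shown is an upper bound, because some halted infusions might still count as complete and the permissive rule might also end some infusions. It is not a bound across baselines: with h = 20%, P(at least 7) falls by 0.285 at b = 0.90 (0.987 to 0.702), by 0.392 at b = 0.80 (0.879 to 0.487) and by 0.362 at b = 0.70 (0.650 to 0.288). The Primary Endpoint as labelled in the Protocol Summary counts patients who received plasma and is not affected.

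**The case against.** The strongest reply is that the two sections form a graded scheme. The halting rule speaks of manifestations of anaphylaxis, not of signs in general. The treatment section speaks of minor reactions, says only that continuation is generally possible, requires a pause and observation first, and treats severe allergic reactions separately. On that reading, isolated itching or hives fall under the first section, and the same signs as part of anaphylaxis fall under the second. The last item on the halting list lends some support: it says that gastrointestinal symptoms may be manifestations of anaphylaxis, which leaves that question to judgment.

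This reading is available, and it may be what was meant. But no section adopts it, and nothing tells staff when hives are isolated and when they manifest anaphylaxis. The support from the last item is limited: it concerns signs outside the named list, and it contemplates a halt before full SAE criteria are met, which favours early action. So the statement that a restart breaches the halting rule holds for that rule as written, not under the graded reading.

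Three further objections stand in part:
- A compliant course always exists, namely to halt and not restart. True, but it leaves the other section's permission without use.
- The probabilities rest on assumed rates, and the range is too wide to inform severity. Accepted; the conclusion does not depend on them.
- The blood pressure point is weak, since a general statement can coexist with specific thresholds. Accepted; it is a lesser tension only.

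**Conclusion.** The concern holds. For itching and hives the protocol gives a conditional permission to continue in one section and an unconditional bar on restart in another, with no precedence, cross-reference or criterion to separate them. It must be fixed, because it is a stated safety rule in conflict and not a missing detail.

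Its extent in the text is two signs. How often it would arise among 10 recipients cannot be derived from the documents; the 9.6% to 89.3% range rests wholly on assumed reaction rates of 1% to 20%. The effect on the completion count is illustrative. The severity rests on the restart conflict alone. Confidence is high, because the point depends only on the two texts.

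**What to change.** Reconcile the plasma administration section with Halting Criteria/Rules for Subject Infusion:

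- Give each sign one stated action, the same in both places.
- State whether the halting list applies to any listed sign alone or only once anaphylaxis is judged present.
- Add a cross-reference between the two sections.

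Which rule should govern is a clinical decision for the investigators; this review takes no position on it.

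An optional clarification is to say whether dyspnea and hypoxemia on the halting list mean a change from the pre-infusion assessment. Worsening of a sign already present is now left to the clinical-judgment item.

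The cost is wording in two sections and one cross-reference. No new assessment, visit or data field is needed.
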